6.13.3.1. Other Secondary and Exploratory Efficacy Analyses

Unless otherwise specified, other secondary and exploratory efficacy analyses will be conducted using EAS. Missing data will be imputed using LOCF or handled through MMRM without utilizing multiple imputation technique.

6.13.3.2. Other Secondary Efficacy Analyses

Table GPHK.6.5. Secondary Measures Not Controlled for Type 1 Error

Objective	Relative to the efficacy measure:	Analysis conducted in a manner similar to:	Additional Information
tirzepatide 5 mg QW is superior to placebo at 72 weeks:	Percentage of participants achieving $\geq 10\%$ (and $\geq 15\%$) body weight reduction from randomization	logistic model in Section 6.13.1.1	None
	Change in waist circumference (cm) from randomization	MMRM model in Section 6.13.1.1	Use baseline waist circumference as a covariate.
	Change in SF-36 v2 acute form Physical Functioning domain (PF) score from randomization	ANCOVA model	with terms of treatment, stratification factors, and baseline SF-36v2 PF score as a covariate. Missing data will be imputed using LOCF.
tirzepatide 5 mg, 10 mg and/or 15 mg QW is superior to placebo at 72 weeks:	Mean change in body weight (kg) from randomization	MMRM model in Section 6.13.1.1	LSM estimates through 72 weeks will be plotted by study treatment.
	Mean change in BMI (kg/m^2) from randomization	MMRM model in Section 6.13.1.1	Use baseline BMI (kg/m^2) as a covariate. LSM estimates through 72 weeks will be plotted by study treatment.
	Mean change in HbA1c (% , mmol/mol) from randomization	MMRM model in Section 6.13.1.1	Use baseline HbA1c (% , mmol/mol) as a covariate. LSM estimates through 72 weeks will be plotted by study treatment.
	Mean change in fasting glucose (mg/dL) from randomization	MMRM model in Section 6.13.1.1	Use baseline fasting glucose as a covariate. LSM estimates through 72 weeks will be plotted by study treatment.
	Mean change in IWQOL-Lite-CT Physical Function composite (PF) score from randomization	ANCOVA model	with terms of treatment, stratification factors, and baseline IWQOL-Lite CT PF score as a covariate. Missing data will be imputed using LOCF method.
tirzepatide QW (all doses combined) is superior to placebo at 72 weeks	Mean change in DBP (mmHg), LDL-C (mg/dL), VLDL-C (mg/dL), total-cholesterol, free fatty acids (mg/dL) from randomization	MMRM model in Section 6.13.1.1	All tirzepatide doses will be pooled together. LSM estimates through 72 weeks will be plotted by study treatment.

Secondary Measures Not Controlled for Type 1 Error

Objective	Relative to the efficacy measure:	Analysis conducted in a manner similar to:	Additional Information
tirzepatide 5 mg QW (for participants with prediabetes at randomization) is superior to placebo at 176 weeks	Mean percent change in body weight from randomization	MMRM model in Section 6.13.1.1	Only for participants with prediabetes at randomization in the EAS. Model terms will include treatment group, visit, and treatment-by-visit interaction, country/pooled country, sex as fixed effects, and baseline body weight as a covariate.
tirzepatide 5 mg, 10 mg, and/or 15 mg QW is superior to placebo (for participants with prediabetes at randomization) at 176 weeks	Percentage of participants achieving $\geq 5\%$ body weight reduction from randomization	logistic model in Section 6.13.1.1	same as above
tirzepatide (all doses combined) is superior to placebo (for participants with prediabetes at randomization) at 176 weeks:	Mean change in SF-36v2 acute form physical functioning domain (PF) score from randomization	MMRM model in Section 6.13.1.1	same as above but using baseline SF-36 v2 acute PF score as a covariate.
	Mean change in IWQOL-Lite-CT Physical function composite (PF) score from randomization	MMRM model in Section 6.13.1.1	Similar to above but using baseline IWQOL-Lite-CT PF score as a covariate.

Abbreviations: ANCOVA = analysis of covariance; BMI = body mass index; DBP = diastolic blood pressure; HbA1c = hemoglobin A1c; IWQOL-Lite-CT = Impact of Weight on Quality of Life-Lite-Clinical Trials Version; LDL-C = low-density lipoprotein cholesterol; LOCF = last observation carried forward; LSM = least squares mean; MMRM = mixed model for repeated measures; QW = once-weekly; SF-36v2 = Short Form 36 version 2 Health Survey; VLDL-C = very low-density lipoprotein cholesterol.

6.13.3.3. Exploratory Efficacy Analyses

Table GPHK.6.6. Exploratory Efficacy Analysis

Objective	Relative to the efficacy measure:	Analysis Conducted
compare tirzepatide 5 mg, 10 mg, and/or 15 mg with placebo at 72 weeks	Percentage of participants achieving $\geq 25\%$ body weight reduction from randomization	logistic model in Section 6.13.1.1
compare tirzepatide 5 mg, 10 mg, and/or 15 mg with placebo at 72 weeks	Percentage of participants whose BMI shifts between clinically relevant categories, i.e., from baseline (<25, 25 to <30, 30 to <35, 35 to <40, ≥ 40) to postbaseline (<25, 25 to <30, 30 to <35, 35 to <40, ≥ 40)	Shift analysis will be conducted based on data from EAS.

Exploratory Efficacy Analysis

Objective	Relative to the efficacy measure:	Analysis Conducted
compare tirzepatide 5 mg, 10 mg and/or 15 mg with placebo at 176 weeks	Same as above	Shift analysis will be conducted for the participants with prediabetes at randomization from EAS.
visualize tirzepatide 5 mg, 10 mg and/or 15 mg with placebo percent weight loss change from randomization up to safety follow-up after 72 weeks	Percent body weight loss measured at postbaseline from randomization to 72 weeks plus 4 weeks safety follow-up	Time-course plot will be generated. Only the participants who complete the 72 weeks treatment and have the safety follow-up (Visit 801) will be included.
compare tirzepatide QW (all dose combined) with placebo at 72 weeks	Percentage of participants change in glycemic category, that is, from baseline (normoglycemia, prediabetes, T2DM) to postbaseline (normoglycemia, prediabetes, T2DM)	Shift analysis will be conducted based on data from EAS.
compare tirzepatide QW (all dose combined) with placebo at 176 weeks	Same as above	Shift analysis will be conducted for the participants with prediabetes at randomization from EAS.
compare tirzepatide QW (all doses combined) to placebo (for participants with prediabetes at randomization) at 176 weeks):	
 SF-36v2 acute form Role-Emotional domain (RE) SF-36v2 acute form Mental Health domain (MH) IWQOL-Lite-CT total score IWQOL-Lite-CT Physical composite score IWQOL-Lite-CT Psychosocial composite score EQ-5D-5L utility score EQ-5D-5L VAS score 	Only data from participants with prediabetes at randomization from EAS will be included. MMRM model with terms of treatment (tirzepatide combined, placebo), visit, treatment-by-visit interaction, country/pooled country, sex, and corresponding baseline score as a covariate.

Abbreviations: BMI = body mass index; EAS = Efficacy Analysis Set; IWQOL-Lite-CT = Impact of Weight on Quality of Life-Lite-Clinical Trials Version; MMRM = mixed model for repeated measures; QW = once weekly; T2DM = type 2 diabetes mellitus; VAS = Visual Analog Scale.

In addition, the following endpoints, risk difference in proportions for an unconditional treatment effect (Ge et al.2011) among each tirzepatide dose and placebo arm may be conducted:

- percentage of participants achieving at least 5% body weight reduction at 72 weeks
- percentage of participants achieving at least 10% body weight reduction at 72 weeks
- percentage of participants achieving at least 15% body weight reduction at 72 weeks
- percentage of participants achieving at least 20% body weight reduction at 72 weeks.

6.14. Safety Analyses

Unless specified otherwise, safety assessments will be based on the SS (Table GPHK.6.1). All events that occur between the first dose date of study drug and the end date of study participation will be included, regardless of the adherence to study drug.

The statistical assessment of homogeneity of the distribution of categorical safety responses between tirzepatide doses and placebo will be conducted using Fisher's exact test, unless specified otherwise.

For selected continuous safety parameters, the mean change from baseline differences vs. placebo will be assessed via a MMRM using REML. Data from scheduled visits will be utilized for this analysis. Unless specified otherwise, the model for the analysis during 72 weeks treatment period will include country/pooled country, sex, prediabetes status at randomization, treatment group, visit and treatment-by-visit interaction as fixed effects, and baseline value of the safety parameter as a covariate. For the analysis during the 176 weeks treatment period (or 193 weeks), only participants with prediabetes at randomization in the SS will be included, and the model will contain the terms of country/pooled country, sex, treatment group, visit and treatment-by-visit interaction as fixed effects, and baseline value of the safety parameter as a covariate. To model the covariance structure within participants, the unstructured covariance matrix will be used. If this model fails to converge, the covariance structures specified in Section 6.13.1.1 will be tested in order until met convergence. If the data does not warrant the MMRM model, then ANCOVA model will be conducted.

For selected safety parameters, time-to-first-event analysis via the Cox-proportional hazards model may be conducted. Participants without the event will be censored at the end of study participation. For participants experiencing the event, the "time-to-first-event" will be the time (in days) from first dose to first occurrence of the event.

Where necessary, the rate of events will be analyzed using a generalized linear mixed-effects model assuming the number of events follow a negative binomial distribution and with treatment as a fixed effect. The logarithm of days during the active treatment period will be adjusted as an offset to account for possible unequal treatment duration of follow-up between participants.

Unless otherwise specified, all the analyses listed in this section will be conducted using SS in the following 2 postbaseline periods, respectively:

- up to 72 weeks treatment period plus the safety follow-up (Visit 801, if applicable) for all randomized participants, and
- up to 176 weeks treatment period plus the safety follow-up (Visit 801 or Visit 802) for participants with prediabetes at randomization.

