7.2. Participant Discontinuation/Withdrawal from the Study

To minimize the amount of missing data and to enable assessment of study objectives as planned in the study protocol, every attempt will be made to keep participants in the study irrespective of the following:

- adherence to or discontinuation from study drug
- adherence to visit schedule
- missing assessments
- study drug discontinuation due to AE
- development of comorbidities
- development of clinical outcomes

The circumstances listed above are *not* valid reasons for discontinuation from the study.

[figure not shown]
Participants will be withdrawn from the study in the following circumstances:

- enrollment in any other clinical study involving an IP or enrollment in any other type of medical research judged not to be scientifically or medically compatible with this study
- participation in the study needs to be stopped for medical, safety, regulatory, or other reasons consistent with applicable laws, regulations, and good clinical practice (GCP)
- participant requests to be withdrawn from the study and clearly indicates that there will be no further contact of any kind with the site
- Female participants will be withdrawn from the study if the participant becomes pregnant.

Participants who agree to provide information relevant to any trial endpoint at the end of the study are not considered to have discontinued from the study.

[figure not shown]
Participants discontinuing from the study prematurely for any reason should complete AE and other safety follow-up per Section 1.3 (Schedule of Activities), Section 8.3 (Adverse Events and Serious Adverse Events), and Section 8.2 (Safety Assessments) of this protocol.

7.2.1. Participant Disposition and Timing of Safety Follow-up for the Primary Endpoint (72 Weeks)

Abbreviations: ED = early discontinuation of treatment; Pt = participant; wks = weeks.

7.2.2. Participant Disposition and Timing of Safety Follow-up for those with Prediabetes at Randomization Continuing in Additional 2-year Treatment Period

Abbreviations: ED = early discontinuation of treatment; wks = weeks.

Note: Participants with prediabetes at randomization who discontinue study drug on or before Week 72 are not eligible to continue in additional 2-year treatment period after Visit 21 (Week 72) and should proceed to V801.

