9.2. Sample Size Determination

Approximately 3429 participants will be screened to achieve 2400 randomly assigned to study intervention (600 participants per intervention group).

The sample size determination assumes that evaluation of superiority of 10-mg tirzepatide and tirzepatide 15 mg to placebo will be conducted in parallel, each at a 2-sided significance level of 0.025 using a 2-sample t-test. Additionally, a difference of at least 11% mean body weight percentage reduction from randomization at 72 weeks for 10-mg tirzepatide and/or tirzepatide 15 mg compared with placebo, a common SD of 10%, and a dropout rate of 25% are assumed for statistical power calculations. Under the assumptions above, randomizing 2400 participants in a 1:1:1:1 ratio to tirzepatide 5 mg (600), tirzepatide 10 mg (600), tirzepatide 15 mg (600), and placebo (600) provides more than 90% power to demonstrate superiority of tirzepatide 10 mg and/or 15 mg to placebo.

The chosen sample size and randomization ratio also provides >90% power to establish superiority of 10-mg tirzepatide and 15-mg tirzepatide doses to placebo in term of percentage of participants achieving at least 5% body weight reduction at 72 weeks, conducted in parallel using a Fisher's exact test, each at a 2-sided significance level of 0.025, assuming 25% placebo-treated participants and 90% tirzepatide-treated participants achieving the goal and a dropout rate of 25%.

In addition, assuming that approximately 60% of the randomized population will have prediabetes, the study sample size will also provide more than 90% power to demonstrate superiority of tirzepatide (all doses combined) over placebo in terms of delaying the onset of diabetes for participants with prediabetes at study entry. It is based on the following assumptions: 1.6% (corresponding to annual hazard rate of 0.54%) of participants randomized to tirzepatide and 6% of participants randomized to placebo (corresponding to annual hazard rate of

2.1%) will progress to diabetes during the 3-year period; 49% of participants will drop out (corresponding to annual drop-out rate of 22%) during the same period; and the test will be conducted at a 2-sided significance level of 0.05.

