9.4.4.2. Adverse Events

Adverse events will be coded from the actual term using the Medical Dictionary for Regulatory Activities (MedDRA) and reported with preferred terms and system organ class. Counts and percentages of participants experiencing events will be reported for each treatment group, and Fisher's exact test will be used to compare the treatment groups.

The percentage of participants experiencing TEAE, SAE, discontinuation due to AE will be summarized by treatment group.

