6.14.1. Analysis of Adverse Events

6.14.1.1. Treatment Emergent Adverse Events

A treatment-emergent adverse event (TEAE) is defined as an event that first occurred or worsened in severity after baseline. The MedDRA Lowest Level Term (LLT) will be used in the

treatment-emergent derivation. The maximum severity for each LLT during the baseline period including ongoing medical history will be used as baseline severity. For events with a missing severity during the baseline period, it will be treated as “mild” in severity for determining treatment-emergence. Events with a missing severity during the postbaseline period will be treated as “severe” and treatment-emergence will be determined by comparing to baseline severity.

For events occurring on the day of first taking study medication, the case report form (CRF)-collected information (for example, treatment emergent flag, start time of study treatment and event) will be used to determine whether the event was pre- versus post-treatment if available. If the relevant information is not available, then the events will be counted as post-treatment.

The counts and percentages of participants with TEAEs will be summarized by treatment using MedDRA PT nested within SOC. Statistical comparisons will be applied at both the SOC and PT levels. Events will be ordered by decreasing frequency within SOC. The SOC will be in alphabetical order. For events that are sex-specific, the denominator and computation of the percentage will include only participants from the given sex.

An overview of the number and percentage of participants who experienced a TEAE, serious adverse event (SAE), death, discontinued from study treatment or study due to an AE, relationship to study drug will be summarized by treatment.

The counts and percentages of participants with TEAEs by maximum severity will be summarized by treatment using MedDRA PT. For each participant and TEAE, the maximum severity for the MedDRA PT is the maximum postbaseline severity observed from all associated LLTs mapping to the MedDRA PT. The maximum severity will be determined based on the nonmissing severities. If all severities are missing for the defined postbaseline period of interest, it will show as missing in the table.

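### The 176-week safety comparisons default to crude Fisher tests despite unequal follow-up, and the SAP assigns its time-to-event and rate models to none of the main adverse event tables

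*SAP*

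**What the plan says.** SAP Section 6.14 sets the default for safety outcomes: "The statistical assessment of homogeneity of the distribution of categorical safety responses between tirzepatide doses and placebo will be conducted using" Fisher's exact test, with room for stated exceptions. Protocol Section 9.4.4.2 agrees for adverse events: "Fisher's exact test will be used to compare the treatment groups". SAP Section 6.14.1.1 fixes the level of testing: "Statistical comparisons will be applied at both the SOC and PT levels".

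The event window runs on or off drug: "All events that occur between the first dose date of study drug and the end date of study participation will be included". These analyses are done for a 72-week period in all randomized participants, and again "up to 176 weeks treatment period plus the safety follow-up (Visit 801 or Visit 802) for participants with prediabetes at randomization".

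Follow-up in that second period is not uniform. The note in Protocol Section 7.2.2 says: "Participants with prediabetes at randomization who discontinue study drug on or before Week 72 are not eligible to continue in additional 2-year treatment" period, and sends these participants to Visit 801. Under Protocol Section 4.1.1.2.5 that visit falls four weeks after the Week 72 visit, or four weeks after early discontinuation for those who decline the Week 72 return. Their observation therefore ends at about Week 76 or sooner. Participants who complete 176 weeks are followed for a further 17, to Week 193. Protocol Section 9.2 expects that "49% of participants will drop out (corresponding to annual drop-out rate of 22%) during the same period", with no split by arm.

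SAP Section 6.14 also offers two methods that use time. One is a Cox model for selected parameters, as an option. The other is a negative binomial rate model, to be used where needed, with log days of active treatment as offset. SAP Sections 6.14.1.4, 6.14.3 and 6.14.3.12 give SAEs, AESIs and malignancy as counts and percentages.

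**The concern.** A crude percentage over 176 weeks mixes the risk per unit time with the length of observation. If one arm is observed for longer on average, it shows more events at the same underlying risk, and a test of crude proportions treats the gap as a difference in risk. In the other direction, shorter observation on tirzepatide hides a true excess.

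Early truncation here is tied to stopping drug, and stopping can depend on treatment, for example through gastrointestinal intolerance or lack of weight loss. Protocol Section 4.2 names long-term safety as one purpose of the extra two years, so these tables carry that question. The SAP already contains suitable methods but does not say which 176-week tables will use them. That choice would be left until the data are known.

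**Working it through.** **Inputs from the documents.** 2400 randomized 1:1:1:1 and about 60% with prediabetes (Protocol Section 9.2): 600 × 0.60 = 360 per arm, or 360 placebo and 1080 tirzepatide. Two-sided alpha 0.05 (SAP Section 6.2). Maximum follow-up 193 weeks: t = 193/52.18 = 3.70 years.

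**The plan's own figures.** Section 9.2 converts three-year percentages to annual hazards by −ln(1 − p)/3. Dropout: −ln(0.51)/3 = 0.224, the stated 22%. Diabetes: −ln(0.984)/3 = 0.0054 and −ln(0.94)/3 = 0.0206, the stated 0.54% and 2.1%. No figure is stated for the adverse event comparisons.

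**Assumptions, not in the documents.** Dropout by arm, adverse event hazard λ, constant hazards, and dropout unrelated to event risk within arm.

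**Crude incidence.** With dropout hazard δ,

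p = λ/(λ + δ) × [1 − exp(−(λ + δ)t)].

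Take dropout of 55% on placebo (δ = 0.266) and 40% on tirzepatide (δ = 0.170), with λ = 0.10 in both arms:
- Placebo: 0.10/0.366 × [1 − exp(−0.366 × 3.70)] = 0.273 × 0.742 = 20.3%.
- Tirzepatide: 0.10/0.270 × [1 − exp(−0.270 × 3.70)] = 0.370 × 0.632 = 23.4%.

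The ratio is 1.15 at identical risk. Mean time to dropout or Week 193, (1 − exp(−δt))/δ, is 2.35 versus 2.74 years.

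**Fisher rejection rate under equal hazards**, by exact enumeration of two binomials:

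| λ per year | Crude, placebo vs tirzepatide | One dose vs placebo (360 vs 360) | Pooled doses vs placebo (1080 vs 360) | One dose, dropout 49% in both |
|---|---|---|---|---|
| 0.10 | 20.3% vs 23.4% | 15.2% | 22.2% | 4.1% |
| 0.05 | 10.9% vs 12.6% | 9.0% | 12.6% | 3.8% |
| 0.02 | 4.6% vs 5.3% | 5.2% | 6.8% | 3.3% |
| 0.01 | 2.3% vs 2.7% | 3.8% | 4.7% | 2.9% |
| 0.005 | 1.2% vs 1.4% | 2.3% | 3.4% | 1.9% |

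The crude ratio stays at 1.15 to 1.17 in every row. For rare events the test rarely rejects, but the estimate is just as biased.

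**Other splits**, one dose versus placebo, for true three-year risks of 10%, 20% and 30%:
- 55% vs 47% (weighted mean (55 + 3 × 47)/4 = 49%): 4.7%, 6.3%, 7.9%.
- 60% vs 45.3% (also 49%): 7.5%, 12.5%, 18.0%.
- Week 72 truncation alone, 30% vs 20% stopping by then: 4.7%, 6.1%, 7.6%. At 35% vs 15%: 7.6%, 12.9%, 18.6%.

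**Masking.** True hazard ratio 1.5, three-year placebo risk 20%. With 45.3% dropout in both arms, crude incidence is 17.2% vs 24.5% and Fisher power is 63%. With 60% dropout on tirzepatide it is 17.2% vs 21.0% and power falls to 22%. Most of that fall is bias rather than lost events. A log-rank test on the same 360 × (0.172 + 0.210) ≈ 138 events has power of about Φ(√(138/4) × ln 1.5 − 1.96) = Φ(0.42) = 66%.

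**The alternative.** Under 55% vs 40% dropout and equal hazards, a simulated log-rank (Cox score) test, one dose versus placebo, 8000 runs, rejects in 4.8% at λ = 0.10 and 5.0% at 0.05.

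**Why person-year rates do not serve everywhere.** Let a 20% risk fall entirely in Weeks 0 to 20, equal in both arms, with the same dropout split. Crude incidence is 19.0% vs 19.4%, ratio 1.02. Mean time at risk to first event, dropout or Week 193 is 1.92 vs 2.23 years. The rates are then 9.9 vs 8.7 per 100 participant-years, a false ratio of 0.87 in favour of tirzepatide.

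**The case against.** The strongest reply is that the SAP does not ignore the problem. Its rate model is there to handle unequal follow-up. Hypoglycemia and injection-site reactions already get rates (SAP Sections 6.14.3.6 and 6.14.3.9), and gastrointestinal events get prevalence over time and time to onset (6.14.3.4.1). Duration of follow-up or exposure by arm and a time-to-event analysis of treatment discontinuation are planned (6.11.1, 6.11.2), so an imbalance would be visible. A 72-week safety analysis in all participants stands beside the 176-week one. Fisher's test is a default that can be overridden, and safety tests carry no multiplicity control (6.6) and drive no formal decision. All this stands, and it narrows the point to one of assignment.

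The dropout gap is also an assumption. The 49% was set for the diabetes power calculation, and 55% versus 40% averages (55 + 3 × 40)/4 = 43.75%, not 49%. Protocol Section 7.1 asks participants who stop drug to keep attending visits. This too stands. Attendance cannot lengthen follow-up past about Week 76 for prediabetes participants who stop by Week 72, but that rule applies equally to every arm and does not by itself create a difference.

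A reader might infer that the 176-week Fisher tests are invalid, or that false safety signals are to be expected. The documents do not support that. They give no dropout by arm, equal dropout keeps the test below 5%, and a small gap inflates it only modestly. Nor does the 22% for pooled doses describe the default test, which Section 6.14 frames as doses against placebo.

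**Conclusion.** The point holds as a gap in pre-specification. For the 176-week period the default comparison ignores time at risk, follow-up ranges from about Week 76 or sooner to about Week 193, and the methods that would deal with this are not assigned to the TEAE, SAE, AESI or malignancy tables.

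Its size depends on a difference in dropout that the documents do not state. At 55% versus 40%, rejection for one dose versus placebo is about 15% at a hazard of 0.10 per year, about 9% at 0.05, and near or below nominal at 0.02 or less. Pooled figures are about 22% and 13% at the two higher hazards. With equal dropout there is no inflation. The direction is unknown in advance: a false difference or a masked excess.

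The figures rest on constant hazards and non-informative censoring. Events clustered in dose escalation are little affected, and late events more. Kaplan-Meier and Cox share the censoring assumption but not the constant-hazard one. The consequence is for long-term safety interpretation and not for the primary efficacy result.

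**What to change.** In SAP Section 6.14, for the 176-week period in the prediabetes cohort:

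- Change *may* to *will* for time to first event. Give Kaplan-Meier estimates and Cox comparisons, censored at end of participation, for SAEs, AESIs, malignancy and common TEAEs.
- Base comparative statements on these analyses. Keep crude percentages as description.
- Report exposure-adjusted incidence rates only as a supplement. Their time at risk should match the event window, which runs to end of participation, rather than days of active treatment. Do not use them as the comparative basis for early transient events such as gastrointestinal ones.

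End of participation, duration of follow-up and the Cox censoring rule are already defined in SAP Sections 6.2, 6.11.1 and 6.14, so no new data are needed. The cost is a few extra tables.
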